1.0 Background

Glucocorticoids (GCs) are commonly used worldwide to treat several conditions, including asthma, lymphomas, and chronic inflammatory disorders.^{1,2} It is estimated that between 1-3% of the general population in developed countries have used GCs, and that 65-75% of these patients used GCs chronically (≥ 3 months).^{1,3} Although GCs have dramatic anti-inflammatory and immunosuppressive effects, they exhibit **large inter-individual variability in GC response in terms of efficacy and toxicity**. This variability in GC response explains why nearly 30% of patients with different pathological conditions have a suboptimal response to the anti-inflammatory effects of GCs⁴⁻⁷ resulting in morbidity and substantial economic costs.⁸ Moreover, it explains why between 10 to 80% of patients who receive GCs chronically develop serious side effects.⁹⁻¹¹

2.0 Rationale and Specific Aims

The large inter-individual variability in GC response has a genetic component, but the genetic architecture of GC response is still unknown. A few studies have linked a small number of genetic variants with GC therapeutic efficacy.¹²⁻¹⁵ One reason for the lack of progress in identifying the genetic determinants of GC efficacy has been the measurement of response in clinically heterogeneous phenotypes (e.g., asthma, inflammatory bowel disease). These phenotypes require weeks to respond to GCs, and the pharmacogenetic signal is susceptible to confounding by disease heterogeneity and co-therapies. A more attractive approach is to study a “clean” intermediate phenotype — a pharmacodynamic measure of GC efficacy. GC-induced lymphopenia is such a measure; this is a rapid, reproducible, dose- and concentration-dependent response that has been quantified in human pharmacokinetic and pharmacodynamic models.¹⁶⁻¹⁹ Moreover, lymphocytes are major determinants of inflammation and GCs exert part of their anti-inflammatory effects by altering lymphocyte kinetics and survival. Thus, GC-induced lymphopenia is a robust and relevant intermediate phenotype to study the genetic predictors of GC efficacy.

In addition to variability in GC efficacy, there is also marked variability in the frequency and severity of GC toxicity. One of the most common metabolic side effects of GC therapy is GC-induced glucose intolerance.²⁰⁻²² Although GC impairs glucose metabolism through insulin resistance and by β -cell dysfunction, there is large variability in the severity of the metabolic effects of GCs that is explained by clinical factors. Evidence suggest that metabolic effects of GC has a genetic component, but the genetic determinants of metabolic toxicity remains unknown.

As other complex traits, genome-wide association studies (GWAS) have identified some risk variants for GC response;¹²⁻¹⁵ however the functional relevance for most of these variants are not known. In complex traits, the combination of GWAS information and large gene expression data has shown that top hits on GWAS were enriched for polymorphisms that regulate expression levels of genes (regulatory polymorphisms),²³ and that these regulatory variants explained a large proportion of the phenotypic variability for complex phenotypes including drug response.^{24, 25}

GCs are known to exert their effect through changes in gene expression and also by interacting with several transcription factors,^{26,27} but we still do not know which genes are involved in the response to *in vivo* administration GC in humans, and which genetic variants are more likely to affect the expression of these genes. Thus, we propose **to perform a hypothesis-generating pilot study to identify potential set of genes and**

regulatory variants that are likely to be involve in the response to GC in terms of efficacy and metabolic toxicity.

For this pilot study we plan to use a robust pharmacodynamic effect of GCs (GC-induced lymphopenia) and a common metabolic complication of GC therapy (GC-induced glucose intolerance) after *in vivo* administration of GC as our clinical phenotypes to:

Specific Aim: To characterize gene expression patterns that are predictive of *in vivo* GC response, and identify regulatory variants that are associated with *in vivo* GC response by challenging 40 healthy volunteers with 60 mg of oral prednisone. We will measure changes in lymphocyte counts and changes in glucose regulation (using the 75 gr glucose tolerance test ~ OGTT) as surrogates of GC efficacy and metabolic toxicity. We will perform transcriptome-wide next generation RNA sequencing to measure changes in gene expression due to *in vivo* administration of GC and study the association of gene expression patterns with our clinical phenotypes. Once we identify a set of genes that are significantly changed after *in vivo* GC administration, we will select potential regulatory variants that have been associated with changes in expression of these genes in public available expression quantitative trait loci (eQTL) datasets to perform genome interrogation and eQTL analysis. This will allow us to identify variants that are associated with gene expression changes due to *in vivo* administration of GC.

3.0 Animal Studies and Previous Human Studies

Pharmacodynamic measures of GC efficacy: One of the mechanism through which GC exerts its anti-inflammatory effects is by modifying the traffic and function of immune cells.^{18,28,29} GCs markedly increase the number of circulating neutrophils and decrease the number of circulating white blood cells (WBC).^{30,31} Among WBC, neutrophils and lymphocytes have been largely use to study the pharmacodynamics of GCs;^{16,17,32,33} mostly because the other leukocytes represent a small percentage of the circulating WBC and the administration of GCs reduced greatly their number (sometimes to undetectable levels) making difficult to establish a dose-concentration response.³¹ Not only the changes induced by GCs in circulating neutrophil and lymphocyte counts are dose- and concentration-dependent,³⁴ reproducible,³⁵ and obtained with equivalent doses of commonly used GCs;¹⁶ but also the same response can be evoked in healthy individuals and in patients with inflammatory disorders.^{34,36,37} Thus, changes in WBC counts are well-established and reproducible pharmacodynamic phenotypes to study the genetics of GC response.

Metabolic side effects of GCs – glucose intolerance: There is also large variability in GC toxicity. Glucose intolerance is a frequent and clinically relevant metabolic complication of GC therapy^{21,22} that can lead to transient hyperglycemia³⁸ or to a permanent condition called GC-induced diabetes.^{39,40} The mechanisms through which GCs induce glucose intolerance are similar to those involved in the development of type 2 diabetes mellitus (T2DM),^{39,41,42} and include insulin resistance⁴³ and β -cell dysfunction.^{44,45} Hyperglycemia occurs when β -cell failure can no longer compensate for the degree of insulin resistance. Clinical studies have shown that short-term administration of GCs impairs glucose tolerance in individuals with normal glucose tolerance;^{44,46-48} while a high single doses of GCs have shown to increase insulin resistance^{44,46,48,49} and consequently increase insulin secretion^{44,46} a compensatory mechanism that is reduced in individuals at risk for T2DM.^{44,48,50-53} Evidence suggest that

glucose intolerance during GC therapy is in part due to a genetic component since the degree of glucose intolerance varies markedly among patients who received the same dose of GCs;⁵⁴ there is large variability in the incidence of glucose intolerance due to GC therapy among races;^{55,56} and variants known to affect GC sensitivity have been associated with metabolic phenotypes⁵⁷⁻⁶⁵ Despite these observations, the genetic determinants of GC-induced metabolic toxicity are not known and we cannot predict who will develop a metabolic complication during GC therapy.

GC exert their effects through the regulation of gene expression by regulatory variants: GCs are known to exert their effect through changes in gene expression and by interacting with several transcription factors. Thus, they represent an excellent tool to study gene-environment interactions.⁶⁶ Accordingly, using immortalized and cultured human [peripheral blood mononuclear cells \(PBMCs\)](#), several studies have shown that GC response is associated with different patterns of transcriptional response,^{14,27,67} and that variants in regulatory binding sites at GC-targeted genes may play a role in GC response variability.^{12,14,26,27} However, the process of immortalization and the culture of cells are known to affect the gene expression response and likely differ from *in vivo* expression.⁶⁸⁻⁷⁰ Moreover, the eQTL studies using immortalized cells have little overlap with eQTL from cultured cells.²⁷ To our knowledge, there is only one small study that has examine gene expression changes with *in vivo* administration with GC but have not performed eQTL analysis. Olnes explored genome transcription response after *in vivo* administration of GCs using whole transcriptome microarrays,⁷¹ and found that peak changes in gene expression were observed 4 hours after GC administration with large variability in the gene expression changes. We propose to extend Olnes' work by studying the role that genetic variants have in the observed variability of gene expression response during *in vivo* administration of GC. Besides, we propose to study PBMCs gene expression response to a glucose challenge due to *in vivo* administration of GCs to study the genetic architecture of the metabolic complications of GC administration, which has not be done.

4.0 Inclusion/Exclusion Criteria

Inclusion criteria:

- 18 to 45 years old (to exclude the effect of age on glucose tolerance)
- BMI between 20 and 30 kg/m² (to exclude individuals that are likely to have impaired insulin response)
- Normal fasting glucose
- Stable weight for three months before participation

Exclusion criteria:

- BMI ≥ 30 kg/m²
- Fasting glucose ≥ 126 mg/dl
- Shift work or disordered sleep (to exclude individuals with alterations in the hypothalamus-adrenergic axis)
- Any active diseases (requiring current treatment)
- Use of any medication regularly (including over-the-counter such as aspirin, ibuprofen, etc)
- Previous exposure to GCs (within the last year)
- Diabetes
- Pregnant or breastfeeding

5.0 Enrollment/Randomization

We plan to recruit participants by sending notices through ResearchMatch.org, Research notifications email, word of mouth, and fliers.

6.0 Study Procedures

Potential participants will meet with the study team to discuss the purpose, inclusion and exclusion criteria, procedures and risk/benefits of the study. Those who sign the consent form will come for a screening visit, and if they fulfill inclusion and exclusion criteria, they will come to Vanderbilt University Medical Center (VUMC) for two study visits in the following 30 days. The study visits will take place within a one-month window, will start early in the morning and will last approximately 6 hours. For all the study visits participants will be asked to fast overnight and avoid alcohol consumption and exercise (except walking < 30 minutes) 48 hours before the visit, and be free of any illness.

- Screening visit: The participant will arrive fasting early in the morning to VUMC. In this visit, the study team will ask questions about his/her health and past medical history. The study team will perform a brief physical exam that include participant's height and weight to calculate the body mass index (BMI) and waist and hip circumference. Blood samples will be collected for safety reasons and to culture peripheral blood mononuclear cells *in vitro* with glucocorticoid. We will request a urine and stool sample for future research. Women of child-bearing potential will have a urine pregnancy test. Women who are pregnant will not be allowed to participate. The study team will provide instructions about fasting and activities before the study visits. If any of the test results on the blood collected at the screening suggests that the participant may have a condition that can alter the study (e.g., random glucose > 200 mg/dL) or put him/her at risk, the study team will contact the participant to explain the reason why he/she cannot participate in the study.
- Study visit 1: The participant will arrive fasting early in the morning to VUMC. A standardized clinical interview and brief physical examination will be performed. For female participants, a urine sample will be collected for pregnancy testing. A fingerstick will be performed to check fasting glucose level. An intravenous catheter will be placed in one arm for continuous sampling around 3 1/2 hours after the participant arrival. Once venous access is secure, blood samples will be collected at different times. If the fasting glucose is ≥ 126 mg/dl, the participant will be excluded from the oral glucose tolerance test study, and blood will be collected approximately 4 and 6 hours after the fingerstick. If blood glucose is below 126 mg/dl; we will collect blood samples around 4 hours after the patient's arrival. Immediately afterwards, a 75-gram glucose solution will be administered as part of the oral glucose tolerance test (OGTT), and blood samples will be collected at 10, 20, 30, 60, 90, and 120 minutes after glucose ingestion. Participants with 2-hour blood glucose ≥ 200 mg/dl will be excluded. A standard meal will be provided at the end of the study visit.
- Study visit 2: Visit 2 will occur within one month after visit 1. An interview, physical exam, and urine testing in the fasting participant will be performed, as in Study visit 1. A single dose of 60 mg of oral prednisone will be administered immediately after a fingerstick for blood glucose is performed. Approximately 3 1/2 hours later, an intravenous catheter will be placed in one arm for continuous sampling. The first blood

collection will be performed around 4 hours after the ingestion of prednisone, and immediately after an OGTT will be performed (if tolerated on study visit 1). Blood collection will occur at 10, 20, 30, 60, 90, and 120 minutes after glucose ingestion. A standard meal will be provided at the end of the study visit.

Each visit will take approximately 6 hours and the participant should stay at VUMC during the study visits. The study team will contact the participant by phone for the next two consecutive days after the last visit to inquire about any problem related to the study.

Measurements: Blood samples will be used for the following:

- Basic metabolic screening
- Glucose, insulin, and C-peptide to study insulin sensitivity and β cell function^{72, 73} at both study visits.
- Blood cell counts.
- RNA extraction will be performed from PBMCs collected in both study visits.
- Genotyping
- Urine and stool samples will be stored for future research. Female participants will have a urine pregnancy test at each study visit.

RNA sequence and Genotyping: RNA will be extracted from PBMC lysates following standard procedures and send to the Vanderbilt Technologies for Advance Genomics (VANTAGE) Core for RNA-seq. VANTAGE will perform RNA sequencing including small RNAs. Once sequencing data is available, VANGARD will align the reads to a reference genome, count the reads, compared gene expression levels before and after GC exposure and obtain a list of genes that are differential expressed. Genotyping will be performed at the VANTAGE Core using Megachip

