9.0 Study Withdrawal/Discontinuation

Withdrawal of participants from any part or the whole study is under the discretion of the PI and will be done if:

- Performing a specific study procedure may be harmful for the participant or he/she cannot tolerate the procedure.
- The participant does not meet the study requirements
- The study is stopped
- Participant is not willing to continue the study

Participants who may not tolerate the OGTT may continue in the study to assess GC efficacy but not GC metabolic toxicity. The study team will explain to the participant why he/she is taken out from specific procedures or from the whole study.

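### Does the visit 1 rule for fasting glucose of 126 mg/dl or more contradict the study exclusion in section 4.0?

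*Combined protocol and SAP*

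**What the plan says.** Section 4.0 requires normal fasting glucose and lists "Fasting glucose ≥ 126 mg/dl" as an exclusion. It does not say at which visit the value is read.

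Section 6.0 gives the order of events. After a fasting screening visit, "if they fulfill inclusion and exclusion criteria, they will come to Vanderbilt University Medical Center (VUMC) for two study visits".

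At visit 1 a fingerstick is taken, and no drug is given at that visit. "If the fasting glucose is ≥ 126 mg/dl, the participant will be excluded from the oral glucose tolerance test study", and for that person "blood will be collected approximately 4 and 6 hours after the fingerstick". Participants below the threshold have the OGTT, after which a second rule applies: "Participants with 2-hour blood glucose ≥ 200 mg/dl will be excluded".

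At visit 2 the prednisone dose "will be administered immediately after a fingerstick for blood glucose is performed", with no consequence attached to the reading. The first draw follows at about 4 hours, and the OGTT is conditional on visit 1.

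Section 9.0 covers removal: "Withdrawal of participants from any part or the whole study is under the discretion of the PI". The same sentence goes on to list grounds on which withdrawal takes place. They include possible harm from a particular procedure and failure to meet the study's requirements. Section 9.0 also lets people who may not tolerate the OGTT stay in for the efficacy part alone. Section 10.0 defines no analysis sets.

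**The concern.** One threshold appears to carry two consequences. Under section 4.0 a participant at 126 mg/dl or more is out of the study. Under the visit 1 text the same participant loses only the OGTT. The reading comes before drug exposure, and nothing at visit 2 makes prednisone depend on glucose, so the text lets a person who meets a listed exclusion be dosed.

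The analysis question follows from this. With no analysis sets in section 10.0, whether such a participant's lymphocyte and RNA data count would be settled case by case. The 2-hour rule adds to the doubt because it does not say what the participant is excluded from. A participant without an OGTT also has a 6-hour draw at visit 1 with no stated partner at visit 2. In a study of 40 volunteers, ad hoc handling of even a few people is worth a look.

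**Working it through.** There is no planned figure to reproduce. The check sets the passages side by side and asks whether they can all be followed for one participant.

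**1. Stage at which each rule acts**

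| Stage | Section | Measurement | Consequence at 126 mg/dl or more |
|---|---|---|---|
| Screening | 4.0, applied through 6.0 | Blood sample, participant fasting | Does not proceed to the study visits |
| Visit 1 | 6.0 | Fasting fingerstick | Out of the OGTT part; draws at about 4 and 6 hours |
| Visit 2 | 6.0 | Fingerstick before prednisone | None stated |

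The first two rows share a number but concern different measurements at different times. An entry criterion and a later procedural rule can use one threshold and lead to different actions. Nobody is subject to both rows on the same reading.

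**2. Is the visit 1 rule a slip?** It names the OGTT study as a component and at once supplies a replacement draw schedule. A sentence meant to end participation would not go on to schedule two more draws. The text therefore implies that the participant stays in the part without OGTT, although it does not say so in terms.

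**3. What happens at visit 2?** The plan states "immediately after an OGTT will be performed (if tolerated on study visit 1"). A person who had no OGTT at visit 1 cannot have tolerated it there, so the condition also leaves this group without an OGTT at visit 2.

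**4. Which samples pair across visits without an OGTT?**

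- Visit 1: about 4 hours and about 6 hours after the fingerstick.
- Visit 2: about 4 hours after prednisone, which directly follows the fingerstick. Every later draw is timed from glucose ingestion. With an OGTT the last one falls at 4 h + 120 min = 6 h; without one, no 6-hour draw is stated.

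Of the two visit 1 draws, 1 has a stated partner (4 h) and 1 does not (6 h). The 4-hour pair supplies the change in lymphocyte count and the log2 fold change in expression used in section 10.0. The metabolic indexes need the OGTT, so this participant has none in any case. Each visit is planned to last about 6 hours, so a late visit 2 draw would fit the day if the team wants it.

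**5. Does section 9.0 conflict with this?** It allows removal from part or all of the study. Removing someone from the OGTT only is removal from a part. If the investigator judges that section 4.0 still bites at visit 1, failure to meet the study's requirements is a listed ground for going further.

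**The case for a change.** The strongest reply is that no sentence limits section 4.0 to screening. Pregnancy, another section 4.0 exclusion, is tested again at each study visit, so a screening-only reading cannot simply be assumed. The clause in section 9.0 on continuing for efficacy is written for intolerance of the OGTT, and a glucose reading is not intolerance. If continuation was intended, section 4.0 would ideally carry an exception.

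Part of this stands. The documents do not say whether the glucose exclusion persists after screening, what the 2-hour rule removes a participant from, or what follows from the visit 2 fingerstick. The pregnancy comparison is less telling than it seems. For a repeat pregnancy test the visit 1 text writes no separate consequence, so section 4.0 is the only guide. For glucose the visit 1 text does write one, and the specific provision can be followed as it stands.

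On the 2-hour rule, an unqualified exclusion a few lines after one limited to the OGTT reads most naturally as exclusion from the study. That is an inference from wording, not a view on what the clinical rule should be.

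The missing analysis sets are a real omission with a limited effect. Lymphocyte and expression analyses can use those with a pre/post pair, and metabolic analyses those with an OGTT at both visits. The same split already follows from the provision in section 9.0 for people who cannot tolerate the OGTT.

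**Conclusion.** The passages can be followed together, so this is missing detail and not a contradiction that alters the study. Four things are left unsaid: whether the section 4.0 glucose exclusion applies after screening, the scope of the 2-hour rule, the analysis sets, and a 6-hour visit 2 draw for participants without an OGTT. Setting them down would be tidier, and the clinical choices among them belong to the investigators.

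No change is required, for three reasons. The group is probably small, since a participant must pass a fasting screen and then read 126 mg/dl or more at visit 1; the documents give no basis for a number. The 4-hour pair that the lymphocyte and expression analyses need exists for anyone kept on the no-OGTT track. And this is a hypothesis-generating pilot in which no estimate or conclusion has been shown to change under either reading.

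The conclusion assumes that eligibility is settled at screening, as the sequence in section 6.0 indicates, and that analysts use each participant for the outcomes on which paired data exist.

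### For participants below 126 mg/dl, section 6.0 times Visit 1 sampling from arrival and Visit 2 sampling from prednisone ingestion, so the paired change carries a one-sided offset of unstated size

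*Combined protocol and SAP*

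**What the plan says.** All references are to the combined protocol and SAP, mainly section 6.0.

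- **Visit 1 (no drug), fasting glucose below 126 mg/dl.** The catheter is placed "for continuous sampling around 3 1/2 hours after the participant arrival". For the first draw, "we will collect blood samples around 4 hours after the patient's arrival", and the OGTT follows directly.
- **Visit 1, fasting glucose 126 mg/dl or above.** There is no OGTT, and "blood will be collected approximately 4 and 6 hours after the fingerstick".
- **Visit 2 (prednisone).** "An interview, physical exam, and urine testing in the fasting participant will be performed, as in Study visit 1". Then: "A single dose of 60 mg of oral prednisone will be administered immediately after a fingerstick for blood glucose is performed". The catheter follows about 3.5 h later, and the first blood "collection will be performed around 4 hours after the ingestion of prednisone, and immediately after an OGTT will be performed".
- **Both visits.** "Each visit will take approximately 6 hours". Each begins in the early morning after an overnight fast. No clock time, fast start, pre-dose duration or sampling window is given. The OGTT sampling grid, counted from the glucose drink, is the same at both visits.

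Section 7.0 plans 6 to 6.5 h of monitoring after the dose. Section 10.0 tests the average log2 fold change at FDR < 0.1 with batch, age and BMI as covariates. It then relates that fold change to the changes in lymphocyte counts and metabolic indexes.

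**The concern.** The only blood test described before the Visit 2 dose is a fingerstick glucose. The screening blood serves safety and cell culture. Visit 1 is therefore the drug-free control for the lymphocyte change, the OGTT indexes and each gene's fold change, and it should differ from Visit 2 only by the drug.

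As written, the preliminary procedures sit inside the 4 h at Visit 1 and outside it at Visit 2. The control sample and control OGTT are then taken earlier after arrival than their Visit 2 counterparts. Visit order is fixed, so the gap has the same sign for everyone and does not average out across participants. Any outcome that moves with time of day or length of fast would have part of that movement credited to prednisone. Variation between people in how long the preliminaries take would also add noise to individual responses. The protocol itself treats such influences as relevant: section 4.0 excludes shift workers and people with disordered sleep, and section 6.0 requires fasting before every visit.

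**Working it through.** **Timeline.** Let t be the time from arrival to the Visit 2 dose, which immediately follows the fingerstick. The documents do not give t.

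- Visit 1, below 126 mg/dl: first draw at 4 h and last OGTT draw at 4 + 2 = 6 h after arrival. This reproduces the stated visit length of about 6 h.
- Visit 2: first draw at t + 4 h and last draw at t + 4 + 2 = 6 h + t. This agrees with about 6 h only if t is small. The 6 to 6.5 h of post-dose monitoring likewise makes the visit at least 6 h + t.
- Offset, Visit 2 minus Visit 1: (t + 4) − 4 = t.
- 126-or-above branch: both visits count 4 h from the fingerstick, so the offset is 0 if the preceding steps take equally long.

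Over an assumed range of t:

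| t (min, assumed) | Visit 2 first draw (h after arrival) | Visit 2 last draw | Visit 1 first / last |
|---|---|---|---|
| 0 | 4.0 | 6.0 | 4.0 / 6.0 |
| 15 | 4.25 | 6.25 | 4.0 / 6.0 |
| 30 | 4.5 | 6.5 | 4.0 / 6.0 |
| 60 | 5.0 | 7.0 | 4.0 / 6.0 |
| 90 | 5.5 | 7.5 | 4.0 / 6.0 |

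**How large could the bias be?** This needs a second assumption, the hourly drift of an outcome with time of day or fasting. For illustration only, take 2 to 5% per hour.

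- At t = 30 to 60 min the bias is 0.5 × 2% = 1% up to 1 × 5% = 5%. At t = 90 min and 5% per hour it is 7.5%. At t = 0 it is nil.
- Approximate standard error of a mean log ratio with 40 participants, ignoring pairing: sqrt(2 × (1/mean count + dispersion)/40). At section 10.0's limits (count 10, dispersion 0.5) this is sqrt(2 × 0.6/40) = 0.17. For an assumed precisely measured gene (high count, dispersion 0.05) it is sqrt(2 × 0.05/40) = 0.05.
- A bias of 1 to 5% is ln(1.01) = 0.010 to ln(1.05) = 0.049, or 0.06 to 0.28 SE in the first case and 0.2 to 1.0 SE in the second. At 7.5%, ln(1.075) = 0.072, or about 0.42 and 1.4 SE.
- Approximate per-gene significance level from section 10.0 (20,000 genes, 100 prognostic, 85% power, FDR 0.1): 85 × 0.1/(19,900 × 0.9) = 0.000475, which requires about 3.5 SE.
- A within-person correlation r multiplies these SE ratios by 1/sqrt(1 − r). At r = 0.5 the largest becomes 1.4 × 1.41 = 2.0 SE.

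**The case against.** The strongest reply is that this is a wording ambiguity in a hypothesis-generating pilot. Times are given as approximate, both visits are said to last about 6 h, and t may be short. Even under the assumed drifts, the bias for a typical gene is a fraction of a standard error and trivial beside a 2.5-fold change. In the gene-phenotype regressions a constant offset goes into the intercept, so only variation in t between people matters, and nothing shows that this is large. The OGTT grid itself is matched; only its starting time moves.

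Most of this stands as a limit on size. Three stronger readings a reader might draw are not supported:

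- *Every Visit 2 minus Visit 1 difference is shifted.* It is not. The 126-or-above branch counts its Visit 1 draws from the fingerstick and so matches the Visit 2 dose. That branch should be small, since section 4.0 lists such a glucose value as an exclusion.
- *The shift in clock time and fasting is established.* It equals t only if arrival and fast-start times are similar at the two visits, which the documents do not fix.
- *The gene list will be contaminated.* The arithmetic does not show this. The assumed biases fall short of the per-gene threshold unless pairing is strong and the drift is at the top of its range.

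What the reply does not remove is the mismatch in time zero for the main cohort. It also offers no remedy in the analysis: visit and drug are fully confounded, so an average offset cannot be separated from the drug effect after collection.

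**Conclusion.** The concern holds for participants below 126 mg/dl, who are the main cohort and the source of the OGTT data. Followed as written, section 6.0 samples the drug-free control earlier after arrival than the prednisone visit by t, with t at or above zero for everyone and no covariate that adjusts for it. Reading this as a shift in time of day and fasting length rests on similar arrival and fast-start times. The size cannot be derived from the documents: both the 0 to 90 minute range and the hourly drift are assumptions. The resulting bias is probably small relative to the lymphopenia and to the fold change used for power. It does not invalidate the study, but it is an avoidable one-sided error that is cheap to remove before data are collected.

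**What to change.** In section 6.0:

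- At Visit 1, time the catheter, first draw and OGTT from the fingerstick for all participants. The 126-or-above branch already does this for its draws, and it matches Visit 2, where the dose immediately follows the fingerstick. The nominal offset is then zero whatever t is. Leave the dose and its timing as they are.
- State that the same procedures precede the fingerstick at both visits.
- Record arrival, fingerstick and actual sampling times at each visit, so that any remaining difference can be described.
- Restate the visit length as about 6 h plus the procedures before the fingerstick.

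The cost is a wording amendment and a Visit 1 longer by t. For 40 participants, an assumed t of 30 to 60 min comes to 40 × 0.5 = 20 up to 40 × 1 = 40 clinic hours in total. No extra samples or participants are needed.
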